11.1.3 Serious Adverse Events (SAEs)

The Principal Investigator shall document all SAEs in a subject receiving study drug or during 30 days following the last dose and must be reported to the Repros Therapeutics Inc. Safety Monitor within 24 hours by Fax or telephone, even if the SAE does not appear to be drug-related. This report should include all available information at the time of notification. This notification should be followed with submitting a SAE Report Form provided by Repros Therapeutics Inc. All additional follow-up reports must be reported to the Repros Therapeutic Inc. monitor as soon as available.

Venous Thromboembolic Events

Venous thromboembolic events (VTE) should be reported to the sponsor as Serious Adverse Events regardless of whether the above-defined SAE requirements are met.

12. Concomitant Medications

Any prescription or over-the-counter medication taken during the study will be recorded in the appropriate section of the CRF. Subject must be on a stable dosage of approved concomitant medications at least 48 hours prior to initial drug administration. Unless medically necessary the dosage of chronic medications should not be changed. Unless medically necessary the addition of new medications should be avoided.

12.1 Prohibited Medications

Use of any of the following medications during the study is prohibited:

- Any testosterone products other than the randomized study treatment
- Aromatase inhibitors (e.g. Anastrozole)
- Clomid
- 5 α -reductase inhibitors
- hCG
- Androgen
- Estrogen
- Anabolic steroid
- DHEA
- Herbal hormone products
- Chronic systemic steroid use (short term use is acceptable)

13. STATISTICAL METHODS

13.1 Determination of Sample Size

As this is a hypothesis-generating study sample size was not determined based on statistical assumptions and calculations. [REDACTED]

13.2 Statistical and Analytical Plan

A Statistical Analysis Plan will be prepared prior to study unblinding which will fully describe the analyses planned for this study.

13.2.1 Interim Analysis

Interim analyses will be conducted after all subjects have been assessed for 6 and 12 months. Although the results will be unblinded, per-subject randomization will not be disclosed to subjects, site personnel and sponsor's clinical research staff to maintain the blind at the subject-level for the duration of the study. The study will not be stopped for claims of efficacy at this analysis. However, the study may be stopped for futility or safety at any time. No adjustments for the interim analyses will be conducted.

13.2.2 Demographics and Subject Characteristics

For all subjects included in this study, subject accountability, baseline demographic and medical history data will be summarized for each treatment group. Summaries for quantitative variables include the sample size, mean, median, standard deviation, minimum, and maximum. Summaries for categorical variables include the number and percent of patients for each outcome. No statistical testing will be performed to compare these factors between treatment groups.

13.2.3 Efficacy Analyses

The analysis of each efficacy endpoint will be conducted in the intent-to-treat (ITT) population, defined as all subjects randomized to treatment with enclomiphene or placebo. The ITT population will be determined prior to unblinding the study data and reasons for any subjects excluded will be explained in the clinical study report. Handling of missing data will be described in the Statistical Analysis Plan (SAP) [REDACTED]

[REDACTED] t will be of interest to investigate various prognostic factors, such as age and diet compliance, to determine how these affect treatment response. Those factors will be noted in the SAP.

13.2.3.1 *Lean Body Mass*

Lean Body Mass (LBM) will be determined by DXA at baseline, 6 months and end of study. The change from baseline in lean body mass will be investigated with at least two measurements:

- Percentage change in LBM
- Change in LBM percentage (%LBM)

[figure not shown]
Subjects are expected to gain LBM and percentage LBM. Within and between treatment group t-tests or appropriate non-parametric methods will assess treatment affect. Descriptive statistics will summarize the results.

13.2.3.2 *Body Strength*

Strength will be assessed over the course of the study by assessments of the maximum Leg and Chest Press weight obtained. These values will be assessed at baseline and weekly. The baseline assessment will be determined at the subject's first gym visit. Analyses will compare the periodic assessments to the subject's baseline. Within and between treatment group t-tests or appropriate non-parametric methods will assess treatment affect. Descriptive statistics will summarize the results.

13.2.3.3 *Waist Circumference*

Careful assessments of waist circumference will detect change in body composition. The change in waist circumference over the duration of the study will be calculated and summarized using descriptive statistics. The change from baseline will be compared within and between treatment groups using a t-test or appropriate non-parametric method.

13.2.3.5 *Testosterone*

For each treatment group, the T and change from baseline in T (visit value minus baseline value) will be summarized at each treatment visit using descriptive statistics (sample size, mean, median, standard deviation, minimum and maximum). The change from baseline in T will be compared within and between treatment groups using a t-test or appropriate non-parametric method.

13.2.3.6 *LH*

For each treatment group, the LH and change from baseline in LH (visit value minus baseline value) will be summarized at each treatment visit

using descriptive statistics (sample size, mean, median, standard deviation, minimum and maximum). The change from baseline in LH will be compared within and between treatment groups using a t-test or appropriate non-parametric method.

13.2.3.7 *Metabolic Parameters*

For each treatment group, the HbA1c, FPG, Insulin, HOMA-IR and Quantose IR assessment of insulin sensitivity and change from baseline will be summarized at each treatment visit using descriptive statistics (sample size, mean, median, standard deviation, minimum and maximum). The change from baseline will be compared within and between treatment groups using a t-test or appropriate non-parametric method.

13.2.3.8 *Change in BMI*

For each treatment group, the weight and change from baseline in BMI (visit value minus baseline value) will be summarized at Week 16 using descriptive statistics (sample size, mean, median, standard deviation, minimum and maximum). The change from baseline in BMI will be compared within and between treatment groups using a t-test or appropriate non-parametric method.

[REDACTED]

[REDACTED]

[REDACTED]

[REDACTED]

[REDACTED]

[REDACTED]

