Statistical Methods:	
Although this study is considered hypothesis generating, a Statistical Analysis Plan (SAP) will be prepared prior to the unblinding of the study that documents all planned analyses and data assumptions. Interim analyses will be conducted after all subjects have been assessed for 6 and 12 months.
 
For all subjects included in this study, subject accountability, baseline demographic and medical history data will be summarized for each treatment group. Summaries for quantitative variables include the sample size, mean, median, standard deviation, minimum, and maximum. Summaries for categorical variables include the number and percent of patients for each outcome.
 
Analyses will focus on descriptive statistics for each efficacy endpoint with between and within treatment comparison conducted. It is hypothesized that subjects treated with enclomiphene will have additional improvements in testosterone, body composition, weight, waist circumference and assessments of metabolic parameters.
 
Safety and tolerability [REDACTED] will be summarized for each treatment group separately. Summaries for quantitative variables include the sample size, mean, median, standard deviation, minimum, and maximum. Summaries for categorical variables include the number and percent of patients for each outcome. Where applicable, statistical testing of the safety data to compare the treatment groups is anticipated.
 
[REDACTED]

[figure not shown]

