7. TRIAL OBJECTIVES AND PURPOSE

The primary objective of this study is to compare the effects of treatment with enclomiphene to placebo, upon anthropometric and metabolic parameters in hypogonadal men undergoing a 6-month diet and 15 month exercise program.

Additional study objectives are to document the differences in testosterone and LH and changes from baseline in symptoms using a selection of subject questionnaires in enclomiphene-treated men compared to placebo. [REDACTED]

[REDACTED]

[REDACTED]

[REDACTED]

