8. TRIAL DESIGN

8.1 Study Design

8.1.1 Overview of Study Design

Protocol ZA-205 is a randomized, double-blind, placebo-controlled multi-center study to compare changes in weight, lean body mass (using DXA), waist circumference, glycemic parameters and scores using various subject questionnaires following treatment with 12.5 or 25 mg enclomiphene or placebo in overweight men with acquired hypogonadotropic hypogonadism and waist circumference ≥ 40 inches (101.6 cm). The study requires 7 clinic visits and is approximately 15 months in duration. Subjects will be provided with a 15 month gym membership and personal trainer, and will exercise for 30-45 minutes three times a week. They will also receive a 6 month commercial diet program. Subjects will be treated for 12 months. [REDACTED]

The study will enroll 45 male subjects, 15 randomized to treatment with enclomiphene 12.5 mg, 15 randomized to enclomiphene 25 mg and 15 randomized to placebo, in a 1:1:1 ratio.

Eligible subjects must have 2 consecutive assessments of morning T at Visit 1 (screening). The assessments must be 2-4 days apart and both must be 300 ng/dL or less. Subjects must also have LH >1.4 and < 9.4 mIU/mL at Screening. Waist circumference must be ≥ 40 inches (101.6 cm). Subjects must not have been treated with testosterone products in the 6 months prior to the study. They must not have used testosterone products for 12 months or longer at any time in the past. Subjects will follow a commercial diet plan and exercise with a personal trainer at least 3 times a week. At clinic visits, clinical laboratory assessments will be performed and subject questionnaires will be administered. Subjects will be called every 2 weeks to check on compliance with their exercise regimen and diet, and solicit adverse events. [REDACTED]

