6.8.1 Lean Body Mass

Lean body mass, bone mass, body fat mass, and percentage of total for each will be determined by DXA at baseline and over time. Pairwise comparisons between treatment groups will be performed using t-tests and Wilcoxon rank-sum tests, as appropriate. Within each treatment group the statistical significance of the change/percentage change from baseline will be based on a paired t-test or Wilcoxon signed-rank test, as appropriate.

For measures obtained by DXA, baseline will be defined as the earliest assessment, regardless of relation to the start of study medication.

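### For lean body mass and strength, Protocol 13.2.3.1 and 13.2.3.2 let within-arm tests assess the treatment effect, although every arm gets diet and training and such tests cannot isolate the drug

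*Protocol*

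**What the plan says.** Protocol 13.2.3.1 (LBM) and 13.2.3.2 (strength) carry the same sentence: "Within and between treatment group t-tests or appropriate non-parametric methods will assess treatment affect". In 13.2.3.1 it follows directly on "Subjects are expected to gain LBM and percentage LBM", which names no arm. Protocol 8.1.1 applies the background programme to everyone: "Subjects will follow a commercial diet plan and exercise with a personal trainer at least 3 times a week". Protocol 8.1.11 adds that 40% of each workout is resistance training.

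The trial's question is otherwise a comparison between arms:
- The primary objective (Protocol 7) is to "compare the effects of treatment with enclomiphene to placebo, upon anthropometric and metabolic parameters".
- The design overview (8.1.1) says the study is "to compare changes in weight, lean body mass (using DXA), waist circumference" and other measures across the two doses and placebo.
- The synopsis states: "It is hypothesized that subjects treated with enclomiphene will have additional improvements in testosterone, body composition, weight, waist circumference". It also says: "Analyses will focus on descriptive statistics for each efficacy endpoint with between and within treatment comparison conducted".

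SAP 6.8.1 and 6.8.2 separate the two kinds of test. For the arms: "Pairwise comparisons between treatment groups will be performed using t-tests and Wilcoxon rank-sum tests, as appropriate". The paired t-test or signed-rank test is described only as testing change from baseline within a group. Significance is declared at a two-sided p of 0.05 or less (Protocol 13.3, SAP 6.1), without multiplicity adjustment (SAP 6.3).

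For testosterone, SAP 6.8.4 keeps the pre-dose baseline and adds a second one, the mean of all screening values. A separate change is calculated from each. Inclusion criterion 4 requires two screening values of 300 ng/dL or less.

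**The concern.** A paired test in an arm that is dieting and training asks whether those men changed. It does not ask whether the drug changed them. By naming it beside the between-arm test as a measure of treatment effect, the protocol opens the way to a familiar error: the dose arm is significant, placebo is not, so the drug works. With 15 men per arm, that split arises easily by chance when all arms share the same true gain.

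The wording is particular to these two endpoints. For waist, testosterone, LH, metabolic parameters and BMI, the protocol says only that changes are compared within and between groups. In the endpoint list (Protocol 10, SAP 5), waist, testosterone, insulin resistance, and weight and BMI carry a comparison with placebo. The LBM and strength items do not.

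SAP 6.8.4 has a related weakness. Men are selected partly because their screening values happened to be low, so later values tend to rise without treatment. Within-arm change from the screening average includes that rise.

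**Working it through.** **No planning figure to reproduce.** Protocol 13.1 says the sample size was not based on statistical assumptions, and the documents give no mean or SD of change for LBM or strength.

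**Inputs from the documents.** 15 subjects per arm, two-sided 0.05, paired t-test within an arm, two-sample t-test between arms.

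**Assumptions.** No drug effect; the same true change in all arms, d = mean change / SD of change, from 0.25 to 1.25; normal and complete data; independent arms.

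**Formulas.** P is the chance that one arm of 15 is significant within itself, from the noncentral t with 14 degrees of freedom and noncentrality d√15.
- A given dose significant, placebo not: P(1 − P).
- At least one of two doses significant, placebo not: [1 − (1 − P)²](1 − P).

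Example at d = 0.5: P = 0.438. The first is 0.438 × 0.562 = 0.246. The second is (1 − 0.562²) × 0.562 = 0.384.

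| d (SD) | P | Given dose yes, placebo no | At least one dose yes, placebo no |
|---|---|---|---|
| 0.25 | 0.147 | 0.126 | 0.233 |
| 0.5 | 0.438 | 0.246 | 0.384 |
| 0.75 | 0.771 | 0.177 | 0.217 |
| 1.0 | 0.949 | 0.048 | 0.051 |
| 1.25 | 0.994 | 0.006 | 0.006 |

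The maxima are 0.250 (d about 0.54) and 0.385 (d about 0.49). At large d the split is rare because nearly every arm is significant, which says no more about the drug.

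**The between-arm test on the same data (simulation).** Its false-positive rate is 0.05 per dose at every d, and about 0.09 for at least one of two doses. Among trials showing the single-dose split, it is significant in 16%, about 10% and 11% at d = 0.25, 0.5 and 0.75. It therefore contradicts the split in about 84% to 90% of them.

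**Testosterone with no drug effect (simulation).** Assumed: population mean 250, 300 or 350, between-subject SD 60, 75 or 90, within-subject SD 40, 55 or 70 ng/dL (27 settings), with men kept only if both screening values are 300 or less.

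| Quantity | Result |
|---|---|
| Upward bias, within-arm change from screening average | 5 to 47 ng/dL |
| False within-arm significance, screening average, n = 15 | about 7% to 16% at mean 250; about 55% in the most extreme setting (mean 350, SDs 60 and 70) |
| False within-arm significance, pre-dose baseline | about 5% |
| Between-arm error, either baseline or two-covariate ANCOVA | about 5% |
| ANCOVA CI width / width for change from pre-dose value | 0.82 to 0.85 |
| ANCOVA CI width / width for change from screening average | 0.97 to 0.995 |

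**The case against.** The strongest reply is that this is one loosely worded sentence. It names within and between tests together, and nothing in the plan says that a within-arm p-value, or a split between dose and placebo, counts as a drug effect. Protocol 13.2 leaves the full description of analyses to the SAP, and the SAP confines the paired tests to change from baseline. The objective and the hypothesis are between-arm, and the study is declared hypothesis generating. All of this stands, and it limits the harm. It does not remove the point, because no visible SAP text says that only the placebo contrast measures the drug.

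The sizes for LBM and strength also depend on an assumed d. Strength, after 12 months with a trainer, may sit at the high end, where the split is rare. The figures assume complete t-tests, whereas the plan allows rank tests after Shapiro-Wilk and carries forward or zero-fills missing values in some analyses. That stands too: the figures are a range under stated assumptions, not a forecast.

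Four stronger readings are tempting and are not supported:
- *The trial lacks a valid test of drug effect, or its formal error rate rises to 38%.* Valid between-arm tests are planned, and no planned decision uses the split.
- *Nothing takes the sentence back.* Text in and after Protocol 13.2.3 and in 13.3 is redacted, so only the visible text can be judged.
- *The pooled 30-subject enclomiphene group makes this worse.* Tested within itself against placebo, it would give a split rate peaking near 42%. But SAP 6.1 lists that group for summaries, and a within-group test on it is an inference.
- *The screening baseline biases the estimated drug effect on testosterone.* Randomised arms share the same selection, so the contrast with placebo is unbiased. SAP 3.1 openly notes that baseline testosterone may exceed 300.

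**Conclusion.** The point holds in a limited form. Protocol 13.2.3.1 and 13.2.3.2 give an uncontrolled within-arm test a role in assessing treatment effect that it cannot fill, and the visible SAP text softens this without correcting it. With no drug effect and a common gain of 0.25 to 0.75 SD, a misleading split appears for a given dose in 13% to 25% of trials and for at least one dose in 22% to 38%. This falls to about 5% or less from 1.0 SD upward. The result rests on the assumed gain, 15 complete subjects per arm and normal data. The consequence is a possible misreading of results in a hypothesis-generating study.

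The testosterone point is secondary. SAP 6.8.4 does not exempt change from the screening average from the paired test, and that test is biased upward under every setting tried. The 55% figure belongs to one extreme setting of 27, and nothing in the documents fixes which setting applies.

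**What to change.** 1. In Protocol 13.2.3.1 and 13.2.3.2, replace the sentence with: *Between-group t-tests, or suitable non-parametric methods, assess the treatment effect; within-group tests describe change from baseline only.*
2. Add to SAP 6.8: *Drug effect is judged only by the enclomiphene-placebo difference, with its 95% CI (Hodges-Lehmann interval where the rank-sum test is used). Paired tests describe change from baseline and are not evidence of a drug effect.*
3. In SAP 6.8.4, do not test within-arm change from the screening average. Use the pre-dose baseline for within-arm change.
4. For between-arm testosterone, name one ANCOVA with the pre-dose value and the screening average as covariates. Amend Protocol 13.2.3.5, which now specifies a t-test or non-parametric method, so that the two documents agree.

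Item 4 corrects no bias. It gives one pre-named analysis in place of two baselines. Under the assumptions above its CI is about 15% to 18% narrower than for change from the pre-dose value, but only about 1% to 3% narrower than for change from the screening average.

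The cost is small edits to three protocol sections and SAP 6.8, with no new data or subjects. Within-arm p-values lose their evidential role, one paired test is dropped and one more model has to be specified.

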13.3 General Statistical Issues

For the efficacy variables, a last observation forward approach will be used to impute missing data in some analyses. If there are no post-baseline efficacy data then a value

of no change will be imputed for the missing efficacy measure. Statistical significance will be declared if the two-sided p-value is ≤ 0.05 . [REDACTED]

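### Carrying the last value forward, or imputing no change, for missing DXA lean body mass usually dilutes a real effect; a likelihood-based model should be the main contrast

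*Protocol*

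**What the plan says.** Protocol 13.3 gives two rules for efficacy variables. First, "a last observation forward approach will be used to impute missing data in some analyses". Second, "If there are no post-baseline efficacy data then a value" "of no change will be imputed for the missing efficacy measure". The visible text does not say which analyses use the first rule. It also does not say whether the second is triggered when a subject lacks data on that measure or on every measure.

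Protocol 13.2.3 leaves missing-data handling to the SAP, and the text straight after that deferral is redacted. In both SAP issues the visible efficacy sections (6.8.1 to 6.8.6) specify t-tests and Wilcoxon tests in all randomized subjects and state no imputation rule. SAP 6.8.3, the end of Protocol 13.3 and Protocol Sections 4 and 9 cannot be read, so everything here concerns visible text only.

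On the measurements, Protocol 13.2.3.1 states: "Lean Body Mass (LBM) will be determined by DXA at baseline, 6 months and end of study". It adds: "Subjects are expected to gain LBM and percentage LBM". Strength is measured far more often: "These values will be assessed at baseline and weekly". On duration, Protocol 8.1.1 states: "Subjects will be treated for 12 months". The study itself runs for about 15 months, to a follow-up visit 3 months later.

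**The concern.** The first post-baseline scan is at Month 6. If the no-change rule is read per measure, which its closing words favour, and if no exit scan is done, every man who leaves before Month 6 enters the lean-mass comparison with a change of exactly zero. The protocol's own expectation is a gain. The filled-in value is then tested as if it had been observed.

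Men who leave after Month 6 have that scan carried forward. This understates an effect that is still growing, is neutral on a plateau, and overstates an effect that fades by the last scan. Which applies depends partly on when end of study falls. If it is the 15-month visit, the scan is about 3 months off drug and a plateau or fade is plausible.

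The effect estimate is the main product of a hypothesis-generating trial. Significance is still declared at 0.05, and Protocol 13.2.1 allows stopping for futility, so a biased estimate has consequences even without a power claim. Two analysts could also obtain different lean-mass results from the same data, depending on how they read 13.3.

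**Working it through.** The plan states no dropout rate, effect size, SD or power, so there is no figure of its own to reproduce.

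**Inputs from the documents.** 15 per arm, hence 30 v 15 for pooled enclomiphene against placebo; two-sided 0.05; scans at baseline, Month 6 and end of study.

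**Assumptions.** SD of change 1; correlation 0.7 between changes at the two scans; half of dropout before Month 6; linear accrual, so Month 6 shows half the final change; dropout unrelated to outcome unless stated. Write p for the dropout share, g for the gain shared by all arms and δ for the drug effect.

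**Estimate, per measure.** An arm with true final mean m is analysed with mean

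(1 − p)m + (p/2)(0.5m) + (p/2)(0) = (1 − 0.75p)m.

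With equal dropout the difference is (1 − 0.75p)δ, whatever g is. For δ = 1 SD:

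| Dropout | 10% | 20% | 30% | 40% |
|---|---|---|---|---|
| Estimated effect (SD) | 0.925 | 0.85 | 0.775 | 0.70 |

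With a plateau reached by Month 6, the factor is 1 − p/2: 0.90, 0.85 and 0.80 at 20, 30 and 40%.

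**Estimate, per subject.** If early leavers with other data are left out of the lean-mass analysis, the factor is (1 − 0.75p)/(1 − 0.5p): 0.94, 0.91 and 0.88 at 20, 30 and 40% with linear accrual, and 1.00 with a plateau. If the baseline scan were itself carried forward, the zero would return.

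**Last scan at Month 15.** Take an effect of 0.5 SD at Month 6 and 1.0 SD at Month 12. Per measure:
- 0.75 SD remaining gives 0.75 − 0.5p: 0.65, 0.60 and 0.55 SD at 20, 30 and 40%.
- 0.25 SD remaining gives 0.25(1 − p) + (p/2)(0.5) = 0.25 SD, which is neutral.
- 0.25 SD remaining with all dropout after Month 6 gives 0.25(1 − p) + 0.5p: 0.30, 0.325 and 0.35 SD, which is inflated.

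**Power, per measure.** 30 v 15, δ = 1 SD, linear accrual, pooled t-test, 40,000 simulated trials:

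| Shared gain g | 20% dropout | 40% dropout |
|---|---|---|
| 0 | 77% | 63% |
| 0.5 SD | 73% | 57% |
| 1 SD | 67% | 48% |
| 2 SD | 53% | 33% |
| Observed cases, any g | 78% | 64% |

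The loss runs from 78 − 77 = 1 point to 64 − 33 = 31 points. It depends on g because zeros mixed with values centred well above zero widen the spread.

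**Unequal dropout, no true effect.** With shares pE on enclomiphene and pP on placebo, the false difference is 0.75(pP − pE)g. At 20 v 40% this is 0.15g: 0.075, 0.15 and 0.30 SD for g of 0.5, 1 and 2 SD, with about 5 to 6%, 7 to 8% and 12 to 13% rejection whichever arm loses more. At 10 v 20% it is 0.075g, and rejection stays at or below 8%.

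**When a real effect is exaggerated.** The bias is −0.75·pE·δ + 0.75(pP − pE)g. It is positive only if pP > pE(1 + δ/g). With g = δ, placebo dropout must be more than double that on enclomiphene.

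**Why a model and not observed cases alone.** Suppose there is no effect, g = 1 SD, 20 v 40% dropout, and men with a poor Month 6 response are likelier to leave. Observed cases are then off by −0.05 to −0.14 SD and per-measure imputation by +0.11 to +0.17 SD. A likelihood analysis stays at 0.00 SD with 4.6 to 4.8% rejection. That dropout mechanism is missing at random by construction.

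**The case against.** The strongest reply is that the plan may be sounder than it looks. Redactions sit exactly where the analyses might be named. The wording of 13.3 implies other analyses without carry-forward, and the visible SAP tests mention no imputation. Nothing visible proves that the lean-mass contrast uses either rule. This stands, and it is why the point is conditional on the rules being applied.

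A second reply is that dilution is measured against an effect as if everyone had stayed on treatment, a target the plan never sets. For a man who has quit drug, diet and gym, zero may be close to the truth. This also stands in part: the target needs stating. But a carried value or a zero is not a measurement of what happened after leaving either.

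Third, the study is exploratory, and the model gains only about 1 to 5 points of power over observed cases. That limits the consequence and does not remove the bias.

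A reader might go further and infer that the rules always favour placebo, that they cost a fixed amount of power, or that the plan has no missing-data method at all. The documents support none of these. Fading effects or heavier placebo dropout reverse the direction, an exit scan cannot be ruled out, the shared gain is unknown, and 13.3 does state a method.

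**Conclusion.** The point holds in conditional form and should be acted on. Where the 13.3 rules are applied to DXA lean body mass, read per measure and without an exit scan, they conflict with the protocol's own expectation for men who leave before Month 6 and usually dilute a real effect. At 10 to 40% equal dropout the loss is about 8 to 30% of a 1 SD effect under linear accrual. It is smaller under the per-subject reading and absent there on a plateau.

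Power loss may be negligible or large, because the shared diet-and-exercise gain is not known. False differences matter only when imbalance and shared change are both large. Weekly strength is less exposed: with uniform dropout times and linear accrual the factor is 1 − 0.5p, or 0.90 at 20% and 0.80 at 40%.

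Every size rests on assumed dropout, trajectory and correlation. Confidence is medium because of the redactions.

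**What to change.** In Protocol 13.3 and SAP 6.8, make the main between-group contrast for repeated-visit outcomes a likelihood-based repeated-measures model on all observed visits:

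- Model baseline as an outcome with a mean common to all arms, so that men with only a baseline value stay in the model. With baseline as a covariate they would drop out. Flag baselines taken after the first dose, which SAP 6.8.1 and 6.8.2 allow, because randomization does not justify a common mean for those.
- Use a small-sample degrees-of-freedom method, and state the missing-at-random assumption and the target effect.
- Name the visit of the main contrast (for DXA, Month 12 or Month 15). For weekly strength, fix a few time points in advance.
- Keep last observation forward and no change only as labelled sensitivity analyses for named endpoints, and say whether no change applies per measure or per subject.
- SAP 6.5 already summarizes early discontinuation by group. Add counts of missing and imputed values by arm, visit and rule.

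The cost is wording and routine modelling of data already planned. The downsides are real. Missing at random cannot be checked, and men with no post-baseline value add almost no information on change. The model is fitted with 15 per arm, skewed laboratory markers need a transformation fixed beforehand, and the power gain over observed cases is only about 1 to 5 points.
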